#### Bio-microscopy (Slit-Lamp)

Where available, total severity scores of bio-microscopy (Slit-Lamp of seven items on grading scale, including lid erythema, lid edema, conjunctiva hyperemia, conjunctiva edema, corneal edema, anterior chamber cells, and anterior chamber flare) will be summarized by treatment for Day 1 (post-dose), using a number of observations, mean, standard deviation, minimum, median, and maximum values. The analysis will be based on the safety population defined in [Section 3.1](#). Note that biomicroscopy is only performed if an Adverse Event is suspected by the Investigator. For those subjects with no bio-microscopy test performed on Day 1, the total severity scores will be set to zero for the purpose of the analysis.

For both study eye and fellow eye, the total severity score at post-dose will be analyzed for differences between AG-920 and active-control groups, using analysis of variance (ANOVA).

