### 9.4.7 Analysis of Safety

External eye exam measures and slit lamp biomicroscopy (if applicable) will be summarized at each measured time point using discrete summary statistics.

Visual Acuity data will be summarized at each time point organized by the age and clinically appropriate test, which may be continuous, categorical or both.

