## 2.9 Statistical Methods

Unless specified otherwise, SAS® Version 9.0 or higher will be utilized to perform the statistical analyses of efficacy and safety measures.

Categorical variables will be summarized in general using frequencies and percentages, whereas continuous variables will be summarized in general using descriptive statistics of number of observations (n), mean, standard deviation (SD), minimum (Min), median, and maximum (Max).

In both data listings and CRF domain data tabulations, subject ID will consist of site number plus the subject screening number in the format of XXX-YYY, where XXX denotes the site number and YYY the subject's screening number within the site.

Hypothesis testing, unless otherwise indicated, will be performed at the 5% significance level. All p-values will be rounded to four decimal places; p-values less than 0.0001 will be presented as '<0.0001' in all tables. All group comparisons from analysis of variance (ANOVA) and/or analysis of covariance (ANCOVA) models will be based on Type III sums of squares. In the case of substantial non-normality, results from non-parametric tests will also be reported. All confidence intervals (CI) will be two-sided with 95% coverage, unless stated otherwise.

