### **5.5 Bio-microscopy**

For those subjects with no bio-microscopy test performed on Day 1, the total severity scores will be set to zero for the purpose of the analysis.

Descriptive and inferential statistics of bio-microscopy (Slit-Lamp) total severity score will be presented by treatment for the post-dose assessments in [Table 6.1.1](#) for the study eye.

Descriptive and inferential statistics of bio-microscopy (Slit-Lamp) total severity score will be presented by treatment for the post-dose assessments in [Table 6.1.2](#) for the fellow eye.

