Table 4.4.6 Incidence of Fellow-Eye Treatment-Emergent AEs Associated with Discontinuations and by Preferred Terminology	Table 14.3.2.3.3
Table 4.4.7 Incidence of Fellow-Eye Treatment-Emergent SAEs by Preferred Terminology	Table 14.3.2.2.3
Table 5.1.1 Summary of Visual Acuity Abnormalities: Study Eye	Table 14.3.4.1
Table 5.1.2 Summary of Visual Acuity Abnormalities: Fellow Eye	Table 14.3.4.2
Table 5.2.1 Summary of External Eye Exam Abnormalities: Study Eye	Table 14.3.5.1
Table 5.2.2 Summary of External Eye Exam Abnormalities: Fellow Eye	Table 14.3.5.2
Table 6.1.1 Summary and Analysis of Slit-Lamp Severity Scores: Study Eye	Table 14.3.6.1
Table 6.1.2 Summary and Analysis of Slit-Lamp Severity Scores: Fellow Eye	Table 14.3.6.2
Table 7.1.1 Summary of Pre-Randomization Concomitant Medication Use: Safety population	Table 14.1.5.1
Table 7.1.2 Summary of Post-Randomization Concomitant Medication Use: Safety population	Table 14.1.5.2
Table 7.1.3 Summary of Post-Treatment Concomitant Medication Use: Safety population	Table 14.1.5.3
Table 7.2.1 Summary of Pre-Randomization Study-Eye Concomitant Medication Use: Safety population	Table 14.1.5.4
Table 7.2.2 Summary of Pre-Randomization Fellow-Eye Concomitant Medication Use: Safety population	Table 14.1.5.5
Table 7.3.1 Summary of Post-Randomization Study-Eye Concomitant Medication Use: Safety population	Table 14.1.5.6
Table 7.3.2 Summary of Post-Randomization Fellow-Eye Concomitant Medication Use: Safety population	Table 14.1.5.7

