## **10 List of Other CRF Data Tabulations (ICH E3 Title for Section 16)**

Final CRF data listings will be numbered with the ICH E3 title as listed below.

Data 1.1 (Listing 16.2.1.1) Inclusion/Exclusion Criteria and Eligibility Check  
Data 2.1 (Listing 16.2.4.1) Demography  
Data 2.2 (Listing 16.2.4.2) Medical History  
Data 2.3 (Listing 16.2.2.1) Protocol Deviations  
Data 3.1 (Listing 16.2.5.1) Dose Administration and Randomization  
Data 4.1 (Listing 16.2.6.2) Visual Acuity  
Data 4.2 (Listing 16.2.6.3) Bio-microscopy and External Eye Exam  
Data 5.1 (Listing 16.2.7.1) Adverse Events  
Data 6.1 (Listing 16.2.4.3) Concomitant Medication  
Data 7.1 (Listing 16.2.1.2) Disposition (End of Study Information)  
Data 8.1 (Listing 16.2.6.1) PI's Anesthetic Effect Assessment

(Table and Listing Shells will be provided upon request.)

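### Minor: the SAP text reports slit-lamp findings only as a zero-filled total of seven ordinal grades, where the protocol calls for discrete summaries

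*SAP*

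**What the plan says.** **Protocol.** Section 9.4.7 states: "External eye exam measures and slit lamp biomicroscopy (if applicable) will be summarized at each measured time point using discrete summary statistics". Section 9.4.1 assigns n, mean, median, SD, minimum and maximum to continuous assessments, and counts with percentages to categorical ones. Appendix 1 grades each sign in ordered categories from none (0) to severe (+3), with a further +4 for anterior chamber cells when a hypopyon has formed. Biomicroscopy is done only when an adverse event is suspected (Table 1 footnote 4; section 6.4.3.2).

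**SAP.** Section 2.9.3 takes as its variable "total severity scores of bio-microscopy (Slit-Lamp of seven items on grading scale": lid erythema and edema, conjunctival hyperemia and edema, corneal edema, and anterior chamber cells and flare. The total is summarized with n, mean, SD, minimum, median and maximum, and the arms are compared by ANOVA in each eye. For the unexamined: "For those subjects with no bio-microscopy test performed on Day 1, the total severity scores will be set to zero". Section 5.5 repeats this: "Descriptive and inferential statistics of bio-microscopy (Slit-Lamp) total severity score will be presented by treatment". The title of Table 6.1.1 is "Summary and Analysis of Slit-Lamp Severity Scores: Study Eye", and Table 6.1.2 is its fellow-eye counterpart.

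Three other places bear on the point. SAP 2.9 has a general default: "Categorical variables will be summarized in general using frequencies and percentages". Subject-level data go to Listing 16.2.6.3, "Bio-microscopy and External Eye Exam". The SAP ends with the note "Table and Listing Shells will be provided upon request", and the shells are not in the document.

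**The concern.** The SAP applies the protocol's set of continuous statistics to categorical grades, and it gives no reason. The external eye exam is named in the same protocol sentence, and SAP 2.9.3 does summarize that by frequency and percent. Only the slit lamp departs.

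Two kinds of information are lost from the summary tables.

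- **Which sign, and how bad.** A sum of seven grades does not say whether one structure was badly affected or several were mildly affected. The difference matters clinically. Protocol 1.2 expects mild, temporary hyperemia with AG-920, and it describes a rare but severe corneal reaction, sometimes with iritis, for the comparator.
- **Whether the eye was examined.** With unexamined children set to zero, a zero can mean a normal slit-lamp examination or none at all, and n becomes the size of the arm rather than the number of examinations.

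A reader who wants to compare graded signs between arms would have to count them from the subject listing.

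**Working it through.** The plan gives no figure to reproduce here and no rates of slit-lamp findings. The numbers below are illustrations on assumed data.

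**Inputs.** Seven items (SAP 2.9.3): six graded 0 to 3, and cells graded 0 to 4 (protocol Appendix 1). Arm size: 60 evaluable / 2 = 30, or 70 enrolled / 2 = 35 (protocol 9.2).

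**Step 1: ambiguity of the total.** The range is 0 to 6 × 3 + 4 = 22.

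- Total 1: 7 patterns, one for each sign.
- Total 2: 7 with one +2, and 7 × 6 / 2 = 21 with two +1, making 28.
- Total 3: 7 with one +3, 7 × 6 = 42 with one +2 and one +1, and 35 with three +1, making 84.

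These counts show that the total is ambiguous. They say nothing about how likely each pattern is.

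**Step 2: two arms with the same table.** If k children have total s and the other n − k have zero, then mean = ks/n and SD = √[(ks² − (ks)²/n)/(n − 1)].

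*Mild-to-moderate case.* One child in one arm has moderate hyperemia (+2). One child in the other has mild hyperemia plus mild lid edema (1 + 1). In both arms k = 1 and s = 2.

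- n = 30: mean 2/30 = 0.07; SD √[(4 − 4/30)/29] = 0.37.
- n = 35: mean 2/35 = 0.06; SD √[(4 − 4/35)/34] = 0.34.
- Median 0 and maximum 2 in both arms.

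*Upper case.* Three children with one severe sign each, against three with three mild signs each. In both arms k = 3 and s = 3.

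- n = 30: mean 9/30 = 0.30; SD √[(27 − 81/30)/29] = 0.92.
- n = 35: mean 9/35 = 0.26; SD √[(27 − 81/35)/34] = 0.85.
- The maximum is 3 in both arms and the ANOVA difference is 0, although children with a severe sign number 3/30 against 0/30.

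**Step 3: is the zero-fill the cause?** Not of this overlap. Among the three examined children per arm alone, both arms still show mean 3.0 and SD 0. The zero-fill is what removes the distinction between unexamined and normal eyes: n reads 30 however many children were examined.

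**Step 4: when the totals differ.** One child with a single +3 against three children with a single +1 each, 30 per arm, gives mean 0.10 in both arms and ANOVA p = 1.00. The SDs are 0.55 and 0.31 and the maxima 3 and 1, so the planned table does hint at a difference. It still does not name the sign.

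**Step 5: choice of denominator for the fix.** One child with a severe sign is 1/3 = 33%, 1/5 = 20% or 1/10 = 10% of those examined (assumed numbers), but 1/30 = 3.3% or 1/35 = 2.9% of the arm. If each arm had one such child, but 3 were examined in one arm and 10 in the other, the examined-only figures would be 33% and 10%. Over 30 per arm both would be 3.3%.

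**The case against.** **The protocol does not prescribe a layout.** A reader might infer that protocol 9.4.7 requires a table by sign, grade and eye. It does not. It asks only for discrete statistics, if applicable, and 9.4.1 leaves fuller method description to the SAP. A frequency table of any abnormality could also qualify. This stands: the per-sign layout is a reasonable way to meet the text, not its literal content. It does not rescue a mean, SD and ANOVA, because 9.4.1 gives those descriptive statistics to continuous assessments.

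**The evidence is incomplete.** Item rows may sit in shells that we do not have, and the SAP 2.9 default could support them. This stands as a limit on the claim. The default is general, though, while the slit-lamp text sets a specific rule on the total. The provision in SAP 2.9 for non-parametric results under marked non-normality would also work on the total.

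**Other outputs overlap.** Each slit-lamp record follows a suspected adverse event, so confirmed signs should reach the adverse-event tables by preferred term and by eye. The expected reactions in protocol 1.2 are themselves largely sign-level terms. Some lid or conjunctival signs may also be counted with the external eye exam: SAP 5.4 names iris, pupil and lens, but Appendix 1 puts both exams under one heading with redacted text. Much of this stands. What it leaves open is the graded sign. Protocol 8.3.2.1 prefers the diagnosis to individual signs where possible, and 8.3.2.3 rates severity by discomfort, not by the Appendix 1 scale.

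**The examples are built to tie.** They are, and nothing in the documents suggests three severe signs in an arm. They show what the table can conceal, not what is expected.

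**Conclusion.** The conflict between protocol 9.4.7 with 9.4.1 and SAP 2.9.3 with 5.5 is real, and the point is minor. As the SAP text and table titles stand, the slit-lamp summary gives no by-arm count of graded signs and does not separate unexamined from normal eyes.

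A reader might go further and infer that a safety signal would be lost from the report. The documents do not support that. Few slit-lamp records are expected, the score feeds no decision rule, the adverse-event tables should capture confirmed signs, and Listing 16.2.6.3 shows the data by subject. Nor can it be said that item-level counts are absent from the shells, only that nothing in the text or titles specifies them.

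The conclusion rests on reading discrete statistics as counts and percentages, which 9.4.1 supports for categorical data. The numerical examples rest on assumed findings and on 30 or 35 children per arm.

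**What to change.** Amend SAP 2.9.3 and 5.5 and the shells for Tables 6.1.1 and 6.1.2 to show, by arm and for each eye:

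1. The number examined out of the safety-population N.
2. For each of the seven signs, the number of subjects at each grade (0, +1, +2, +3, and +4 for cells).
3. A separate row for children not examined, who are not counted as grade 0.
4. For comparing arms, percentages of abnormal grades, and of any moderate or worse sign, over the safety-population N.

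Percentages of those examined may be added as description only. Examination is triggered after dosing by an investigator who is not masked (protocol 3.5 masks only the child and the parent or guardian), so the examined children are a selected subset that may differ between arms.

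The total score and its ANOVA can stay as supplementary or be dropped; the protocol does not require dropping them. If the shells already carry the item rows, check their denominators and the row for unexamined children, and align the SAP wording.

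**Cost.** Wording in two SAP sections and two table shells. The item grades are already needed to form the total, so no new data are collected. The tables become slightly longer.

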### 1.2 *Potential Risks and benefits to human subjects*

Minimal risks are expected with AG-920. Based upon clinical trials conducted to date, expected risks for subjects may include temporary, mild conjunctival/ocular hyperemia, eye pain, instillation site reaction (stinging/burning), and conjunctival hemorrhage upon instillation of the investigational medicinal product (IMP). For any additional information on AG-920 use, please refer to the [Investigator's Brochure](#).

Minimal risks are expected with the comparator, Proparacaine HCl ophthalmic solution. Occasional temporary stinging, burning and conjunctival redness may occur with the use of Proparacaine. A rare, severe, immediate-type, apparently hyperallergic corneal reaction (characterized by acute, intense and diffuse epithelial keratitis, a gray, ground glass appearance, sloughing of large areas of necrotic epithelium, corneal filaments and, sometimes, iritis with descemetitis) has been reported. Allergic contact dermatitis from Proparacaine with drying and fissuring of the fingertips has also been reported. For any additional information on Proparacaine use, please refer to the [Package Insert](#).

As this study is to be conducted in healthy pediatric subjects, there is no anticipated benefit other than the possibility that a subject's participation in the present study may help others in the future to have more options for local anesthesia before ophthalmic procedures.

Any new, unexpected adverse events (AEs) present among subjects in this clinical trial will be communicated to Investigators and to ethics committees or Institutional Review Board (IRBs) in accordance with local regulations.

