**LID**

**Erythema**

None (0)=	Normal, without any redness, or less than mild
Mild (+1)=	A low grade flushed reddish color
Moderate (+2)=	Diffused redness encompassing the entire lid margin
Severe (+3)=	Deep diffused reddish color of lid margins and superior or inferior eyelid

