**Edema**

None (0)=	Normal, no swelling of the lid tissue, or less than mild
Mild (+1)=	Slight diffuse swelling above normal
Moderate (+2)=	General swelling
Severe (+3)=	Extensive swelling of the eyelid(s), with or without eversion of upper and/or lower lids.

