**CONJUNCTIVA****Hyperemia**

None (0)=	Normal. Appears white with a small number of conjunctival blood vessels easily observed.
Mild (+1)=	Prominent, pinkish-red color of both the bulbar and palpebral conjunctiva;
Moderate (+2)=	Bright, scarlet red color of the bulbar and palpebral conjunctiva
Severe (+3)=	“Beefy Red” with petechiae --- Dark red bulbar and palpebral conjunctiva with evidence of subconjunctival hemorrhage

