**CORNEA****Edema**

None (0)=	Transparent and clear or less than mild
Mild (+1) =	Dull glassy appearance
Moderate (+2)=	Dull glassy appearance of epithelium with large number of vacuoles
Severe (+3) =	Stromal edema, localized or diffuse, with stromal striae

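### The seven-item slit-lamp total has no corneal-epithelium item and mentions conjunctival hemorrhage only in the top hyperemia grade, so an isolated epithelial defect may score 0 and a focal hemorrhage 0 or 3

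*SAP*

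**What the plan says.** SAP 2.9.3 (Bio-microscopy) builds a total severity score from seven graded items, "including lid erythema, lid edema, conjunctiva hyperemia, conjunctiva edema, corneal edema, anterior chamber cells, and anterior chamber flare". SAP 2.9.3 and 5.5 give a total of zero to any child who has no slit-lamp examination on Day 1. The totals are summarized by mean, SD, minimum, median and maximum and compared by ANOVA, in Table 6.1.1 for the study eye and Table 6.1.2 for the fellow eye. The examination is done only for a suspected adverse event (Protocol Table 1 and 6.4.3.2).

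Protocol Appendix 1 gives grades for the same seven items:
- **Cornea.** Edema is the only item. The epithelium is mentioned once, at grade +2: "Dull glassy appearance of epithelium with large number of vacuoles".
- **Conjunctival hyperemia.** Grade 0 is described by color and vessels: "Appears white with a small number of conjunctival blood vessels easily observed". Hemorrhage enters only at +3, which also mentions petechiae: "Dark red bulbar and palpebral conjunctiva with evidence of subconjunctival hemorrhage".

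Protocol 1.2 ends its list of expected AG-920 effects with "instillation site reaction (stinging/burning), and conjunctival hemorrhage upon instillation of the investigational medicinal product (IMP". For Proparacaine it describes a rare, severe reaction with "acute, intense and diffuse epithelial keratitis, a gray, ground glass appearance, sloughing of large areas of necrotic epithelium, corneal filaments", sometimes accompanied by iritis.

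Protocol 9.4.7 plans discrete summaries of the slit-lamp findings. Protocol 9.4.1 has categorical assessments tabulated by treatment as counts and percentages.

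**The concern.** Because the slit lamp is used only when a reaction is suspected, its summary should be able to register the reactions that the protocol itself names. Epithelial loss has no item, and hemorrhage has none of its own. An examined child with a real finding could therefore contribute the same zero as a child who was never examined.

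Hemorrhage has a second problem. Two investigators could follow the written grades faithfully and still differ by three points. Only subjects and their parents or guardians are masked (Protocol 3.5, SAP 2.4), so the investigator may know the treatment when choosing the grade for a sign listed as an AG-920 risk.

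What is at stake is how well the slit-lamp tables reflect eye findings by arm. In SAP 5.4 the external eye exam tables cover iris, pupil and lens, so the SAP tabulates graded conjunctival and corneal signs by treatment only in Tables 6.1.1 and 6.1.2.

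**Working it through.** **Maximum of the score.** The plan states seven items but no maximum. The top grades in Appendix 1 are:
- lid erythema 3 ("Deep diffused reddish color of lid margins and superior or inferior eyelid")
- lid edema 3 ("Extensive swelling of the eyelid(s), with or without eversion of upper and/or lower lids")
- conjunctival hyperemia 3
- conjunctival edema 3
- corneal edema 3
- anterior chamber cells 4 (hypopyon)
- flare 3

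The count is seven, as the SAP says. The maximum is 6 × 3 + 4 = 22.

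**Applying the written grades.** Signs not named in a row are taken as absent. For the Proparacaine reaction, the ground-glass cornea is assumed to be graded as corneal edema, +1 to +3. Where iritis is present, cells are taken as +1 to +4 and flare as 0 to +3. Hyperemia, where added to that reaction, is +1 to +3.

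| Finding | Sum | Total |
|---|---|---|
| Isolated epithelial defect, clear cornea | no item applies | 0 |
| Same, with mild hyperemia | 1 | 1 |
| Focal hemorrhage in a white eye, graded by color | hyperemia 0 | 0 |
| Same, graded by the hemorrhage wording | hyperemia 3 | 3 |
| Hemorrhage with mild redness, graded by color | hyperemia 1 | 1 |
| Proparacaine reaction, no iritis | corneal edema 1 to 3 | 1 to 3 |
| Same, with iritis | (1+1+0) to (3+4+3) | 2 to 10 |
| Same, with iritis and hyperemia | (2+1) to (10+3) | 3 to 13 |
| For comparison: mild lid erythema and mild lid edema | 1+1 | 2 |

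Two things follow. Epithelial loss itself adds nothing in any row: the Proparacaine reaction earns its points through edema, cells, flare and redness. An isolated defect also totals less than mild redness and mild swelling of the lid.

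**Weight of the hemorrhage ambiguity.** One child graded 3 instead of 0 moves the arm mean by 3/n. With the planned 30 or so per arm this is 3/30 = 0.10. With 35 (half of 70) it is 3/35 = 0.086. These shifts are small in absolute terms, but most other totals may be zeros assigned by rule.

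The documents do not say how often isolated defects or focal hemorrhages occur, so no expected loss can be calculated.

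**The case against.** A reader might infer three stronger things, and the documents support none of them.

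- **That the scale ignores hemorrhage.** It does not, because the +3 hyperemia grade mentions it. The defect is an ambiguous grade, not a certain zero.
- **That the Proparacaine reaction would score 0 or 1.** As Protocol 1.2 describes it, intense and diffuse with a ground-glass cornea and sometimes iritis, it reaches 1 only at the bottom of its range without iritis. With iritis it scores at least 2. A score of 0 belongs to an isolated defect with a clear cornea, which Protocol 1.2 does not describe.
- **That the safety signal would be lost.** A confirmed reaction is an adverse event. SAP 2.9.3 and 5.3 tabulate these by preferred term, severity, relationship and eye. The secondary endpoints are adverse events and related withdrawals, not this score.

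It can also be said that the choice of signs to grade is instrument design, that no text requires the score to cover every named risk, and that the corneal reaction is rare and belongs to the comparator. In addition, the protocol already plans discrete slit-lamp summaries. Part of the Appendix 1 procedure text is redacted, so an ungraded corneal check may exist there.

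Most of this stands and keeps the point minor. It does not remove it. A redacted check could not enter a total that the SAP limits to seven named items. Severity in the adverse event tables rests on discomfort and interference with everyday activities (Protocol 8.3.2.3 and Table 3), which is not a grade of an eye sign. The discrete summaries of Protocol 9.4.7 are not carried into the SAP, which gives the mean and ANOVA of a sum.

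**Conclusion.** The point holds in a limited form. The total has no item for corneal epithelial damage and mentions conjunctival hemorrhage only within +3 hyperemia. An isolated epithelial defect with a clear cornea may score 0 of 22, the same as an unexamined child. A focal hemorrhage in a white eye may score 0 or 3.

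The effect is confined to Tables 6.1.1 and 6.1.2. No named endpoint changes, and both kinds of event still reach the adverse event tables. The conclusion rests on a literal reading of the visible Appendix 1 grades. The range for the Proparacaine reaction also assumes that a ground-glass cornea is graded as corneal edema. This is a minor, inexpensive improvement.

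**What to change.** 1. In Protocol Appendix 1 and on the slit-lamp form, add a corneal-epithelium item and a conjunctival-hemorrhage item, each either absent/present or graded.
2. State whether hemorrhage without dark red conjunctiva raises the hyperemia grade, so that the 0-or-3 ambiguity does not survive beside the new item.
3. In SAP 2.9.3 and 5.5, report counts by item and grade, and each child's worst grade, by treatment for examined subjects, separately for study and fellow eye. This follows the discrete summaries planned in Protocol 9.4.7.
4. The seven-item sum may still be shown.

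The cost is two extra CRF fields on an examination already done for a suspected adverse event, plus revised table wording. No procedure is added. The one drawback is that a total including the new items cannot be compared with any earlier use of the seven-item sum, unless that sum is reported as well.

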**Table 1: Schedule of Visits and Procedures**

	Visit 1	Visit 2			Follow-Up
	Screening	Screening & Baseline			Phone call
	Day -2 - 0/1 Pre-dose	Day 1			Day 2-5
Procedures		Dose		2 -4 min post last drop	15-60 min post eye exam
		0 sec	30 sec		
Written Assent/Informed Consent	X				
Inclusion/Exclusion Criteria 	X	X 			
Demographics, Systemic and Ocular Medical History	X				
Concomitant Medication Query	X	-----X-----			X
Visual Acuity 	X 				X 
External Eye Exam	X				X
Biomicroscopy 					X 
Randomization		X 			
IMP Administration 		X	X 		
Eye Exam Procedure				X	
Adverse Event Assessment		-----X-----			X

IMP = investigational medicinal product

 Screening may occur on the same day as Visit 2 or up to 3 days previously. If on separate days, inclusion/exclusion criteria should be re-evaluated prior to dosing subject to ensure subject still qualifies.

 If Visit 1 and 2 are not performed on the same day, these assessments must be performed prior to dosing at 0 seconds.

 Age appropriate optotype (if capable) with clinically appropriate test (either Teller acuity charts, Allen pictures, HOTV letters, or Snellen acuity, per standard of care), or reaction to light (if not).

 Biomicroscopy only performed if necessary for a suspected AE

 One dose is 2 drops. First drop administered at 0 seconds and the second drop administered at 30 seconds (2 drops 30 seconds apart).

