### ***9.5 Procedure for accounting for missing, unused, or spurious data***

A minimal amount of missing data is expected in this study because of the short duration and the subjects being in the clinic on Day 1. For the ITT population, any missing data on Day 1 will be imputed using the method of last observation carried forward (LOCF), where the closest non-missing value prior to the missing value will be carried forward and imputed for the missing value. The PP and Safety populations will be based on observed data only (without imputation). Any missing, unused, or spurious data will be noted and explained in the final statistical report.

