## **2.8 Handling of Missing, Incomplete, and Repeat Data**

For efficacy parameters, missing or invalid data for anesthetic effect assessment will be assessed for each subject post dose. Missing values due to either invalid data or early termination will be considered as NO anesthetic effect for the subject.

For safety parameters, missing or invalid data will be treated as missing for the corresponding assessment of a visit.

All data records are identified by study visit and/or assessment time point. Should repeated data records exist within a study visit and/or assessment time point, the first valid data record will be utilized for any statistical analyses of the corresponding study visit and/or assessment

time point. All existing data records including the repeat data records in the study database will be presented in data listings and CRF data tabulations.

Any resultant incomplete or missing data of either efficacy or safety parameters will be treated as missing in the statistical analyses involving these parameters.

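### Children with no slit-lamp exam are scored zero and the arms compared by ANOVA, against the plan's own rules for safety data; the result mainly reflects how many children were examined

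*SAP*

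**What the plan says.** Protocol Table 1, footnote 4, makes the slit-lamp exam conditional: "Biomicroscopy only performed if necessary for a suspected AE". It is scheduled only after dosing, so there is no baseline. SAP 2.9.3 (Bio-microscopy) repeats the condition: "Note that biomicroscopy is only performed if an Adverse Event is suspected by the Investigator". The same paragraph defines a total severity score over seven graded signs, bases it on the safety population, and adds that, where a child had no Day 1 exam, "the total severity scores will be set to zero for the purpose of the analysis". In the study eye and the fellow eye alike, "the total severity score at post-dose will be analyzed for differences between AG-920 and active-control groups, using analysis of variance (ANOVA"). SAP 5.5 carries the zero rule into Tables 6.1.1 and 6.1.2.

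Three other places point the other way:
- Protocol 9.5: "The PP and Safety populations will be based on observed data only (without imputation").
- SAP 2.8: "For safety parameters, missing or invalid data will be treated as missing for the corresponding assessment of a visit". The last paragraph of that section says the same of incomplete or missing safety parameters.
- Protocol 9.4.7 plans discrete summary statistics for slit-lamp data, where applicable. It mentions neither a total score nor an ANOVA.

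Protocol 3.5 and SAP 2.4 limit masking to the child and the parent or guardian.

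**The concern.** A child who was not examined has no slit-lamp grade. Entering zero on all seven signs treats not examined as examined and normal, and no passage states or justifies that step. The tables would then show n, mean and SD as if the whole safety population had been graded.

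The children who are graded are chosen by an investigator who may know the treatment. The arm difference therefore mixes how severe the signs were with how readily children were sent to the slit lamp. Safety and tolerability is the secondary objective, so a reader may take the means and P value at face value.

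**Working it through.** The documents give no examination rate, SD, effect size or power for this score, so there is no figure to reproduce.

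**Inputs**
- Children per arm: 70 randomized 1:1 is 35; 60 evaluable is 30 (Protocol 9.2, SAP 2.5).
- Scale maximum: six signs graded 0 to 3 and anterior chamber cells graded 0 to 4 (Protocol Appendix 1), so 6 × 3 + 4 = 22.
- Significance level: two-sided 0.05 (Protocol 9.4.1).
- Share examined, q: not stated. Assumed 2% to 20%, in keeping with an exam triggered by a suspected event and the minimal risk expected in Protocol 1.2; 50% is added as an extreme.

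**Step 1: how much is filled in.** The share of zero-filled scores is 1 − q, and the expected number examined per arm is 35q. The chance that no child at all is examined, which leaves the ANOVA undefined, is (1 − q)^70.

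| q | Filled in | Examined per arm | No child examined |
|---|---|---|---|
| 2% | 98% | 0.7 | 24% |
| 5% | 95% | 1.75 | 2.8% |
| 10% | 90% | 3.5 | 0.1% |
| 20% | 80% | 7 | about 0 |
| 50% | 50% | 17.5 | about 0 |

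**Step 2: what the P value responds to.** Let k of n children in one arm be examined, each scoring s, and none in the other arm.
- Between-group sum of squares: k²s²/(2n).
- Within-group sum of squares: s²k(n − k)/n, on 2n − 2 degrees of freedom.
- Hence F = k(n − 1)/(n − k). The score s cancels.

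With n = 30 and k = 4, F = 4 × 29/26 = 4.46 and P = 0.039, whether each child scores 1 or 22. If s = 4, the table shows means of 16/30 = 0.53 against 0, the mean among examined children is 4.0, and 56 of the 60 scores are filled in.

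With k = 1, F = 29/29 = 1 and P = 0.32. One child at the scale maximum against all zeros therefore gives a mean of 22/30 = 0.73 and an unremarkable test.

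**Step 3: compare with tests on the count alone.** For 4/30 against 0/30, the uncorrected Pearson statistic is 60 × (4 × 30)²/(30 × 30 × 4 × 56) = 4.29, P = 0.038, almost the ANOVA result. Fisher's exact test gives P = 0.112.

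**Step 4: error rates.** These come from 20,000 simulated trials per setting, 35 per arm, with examined scores assumed equally likely to be 1, 2, 3 or 4.
- Same examination rate in both arms, no true difference: rejection in 0.2%, 1.8%, 4.1% and 4.9% of trials at q = 2%, 5%, 10% and 20%.
- Same score distribution but different examination rates: rejection in 18% (10% vs 20%), 42% (5% vs 20%) and 48% (10% vs 30%).
- A true 1-point difference among examined children, same examination rates: it shrinks to q × 1 = 0.05, 0.10 or 0.20 points at q = 5%, 10% and 20%, with power of 2%, 5% and 8%.

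**The case against.** The best defence is that an exam not due is not missing. If no event is suspected, zero may be a convention for no recorded slit-lamp severity, and a specific rule written twice could override the general ones. This has some force, and the conflict is best described as unreconciled text. But neither document states that reasoning or exempts the score from Protocol 9.5 or SAP 2.8, and the SAP paragraph itself opens by confining the summary to available data. The convention might support a labelled count of abnormal findings; it does not support n, mean, SD and ANOVA for children who were not graded.

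The external eye exam, done in every child, does not rescue the zeros as planned. SAP 5.4 tabulates it under iris, pupil and lens, none of which is in the score. Protocol Appendix 1 puts both exams under one heading, but the procedure text is blacked out, and the SAP does not use the external exam to set the score.

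Three further objections stand and limit the point:
- A reader might infer from ANOVA P = 0.039 against Fisher P = 0.112 that zero-filling manufactures significance. It does not. Pearson on the fully observed count gives 0.038, so the gap reflects Fisher's conservatism. Four examined against none could also be a real signal.
- A reader might infer that ocular signs would vanish. They would still appear in the adverse event tables (4.2.5, 4.2.6, 4.4.1), Listing 7, the reported maximum, which zeros cannot dilute, and the planned Listing 16.2.6.3.
- No decision rule depends on this test.

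**Conclusion.** The point holds as a conflict in the plan and a poor safety summary. SAP 2.9.3 and 5.5 cannot be followed together with Protocol 9.5, SAP 2.8 and Protocol 9.4.7. Following them gives an n that counts ungraded children, a diluted mean and an SD that describes a mixture.

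The size depends on an examination rate the documents do not give. At 2% to 20%, 80% to 98% of scores are filled in. It would be too strong to say that the test runs almost entirely on filled-in data as a fact: at 50% examined, half would be real.

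Nor do the documents support a claim of general type I error inflation. With equal examination rates the test stays at or below about 5% and has very little power. False rejection (18% to 48% in the settings tried) needs unequal examination rates with the same underlying scores. The lack of investigator masking makes that possible, but nothing shows it will happen.

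The primary efficacy conclusion is unaffected. This should be corrected before database lock, but it does not threaten the trial's main result.

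**What to change.** Delete the set-to-zero sentence in SAP 2.9.3 and 5.5, and drop the ANOVA of the total score. In Tables 6.1.1 and 6.1.2 show, by arm and eye, the number and percent examined, then item grades and total score for examined eyes only. Point to Listing 16.2.6.3, already planned in SAP section 10, for the individual data. Give the reason for each exam only if the CRF already records it or it can be linked to the adverse event record; no visible passage shows that it is collected.

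The SAP would then agree with Protocol 9.4.7 and 9.5 and with SAP 2.8. The cost is SAP wording and two table shells, with no new data and no protocol amendment. What is lost is a formal P value that carries little information about severity.
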